The inclusion of female subjects of childbearing potential requires the use of highly effective contraceptive measures. They must have a negative serum pregnancy test at Screening and a negative pregnancy test on the Baseline/Day 1 visit prior to randomization. At minimum, a pregnancy test will be performed 7 days after the last study drug dose. In the event of a delayed menstrual period (over one month between menstruations), a pregnancy test must be performed

to rule out pregnancy. This is true even for women of childbearing potential with infrequent or irregular periods. Female subjects must also agree to one of the following from Screening until 30 days after the last dose of study drug.

- Complete abstinence from intercourse of reproductive potential. Abstinence is an acceptable method of contraception only when it is in line with the subject's preferred and usual lifestyle.

Or

- Consistent and correct use of 1 of the following methods of birth control listed below.
 - Intrauterine device (IUD) with a failure rate of <1% per year
 - Intrauterine hormone-releasing system (IUS) with a failure rate of <1% per year
 - Tubal sterilization
 - Essure micro-insert system (provided confirmation of success by hysterosalpingogram three months after procedure and where permitted and used per local prescribing label)
 - Vasectomy in the male partner (provided that the partner is the sole sexual partner and had confirmation of surgical success 3 months after procedure)

Female subjects who wish to use a hormonally based method must use it in conjunction with a barrier method, preferably a male condom. Female subjects who utilize a hormonal contraceptive as one of their birth control methods must have consistently used the same method for at least three months prior to study dosing. Hormonally-based contraceptives and barrier methods permitted for use in this protocol are as follows:

- Barrier methods (each method must be used with a hormonal method)
 - Male condom (with or without spermicide)
 - Female condom (with or without spermicide)
 - Diaphragm with spermicide
 - Cervical cap with spermicide
 - Sponge with spermicide
- Hormonal methods (each method must be used with a barrier method, preferably male condom)
 - Oral contraceptives (either combined or progesterone only)

- Injectable progesterone
- Subdermal contraceptive implant
- Transdermal contraceptive patch
- Contraceptive vaginal ring

Female subjects must also refrain from egg donation and in vitro fertilization during treatment and until at least 30 days after the end of relevant systemic exposure.

3) Contraception Requirements for Male Subjects

During the study, male subjects with female partners of childbearing potential should use condoms when engaging in intercourse of reproductive potential.

4) Unacceptable Birth Control Methods

Birth control methods that are unacceptable include periodic abstinence (eg, calendar, ovulation, symptothermal, post-ovulation methods), withdrawal (coitus interruptus), spermicides only, and lactational amenorrhea method (LAM). Female condom and male condom should not be used together.

5) Procedures to be Followed in the Event of Pregnancy

Subjects will be instructed to notify the investigator if they become pregnant, or are concerned they may be pregnant at any time during the study, or if they become pregnant within 30 days of last study drug dose. Subjects who become pregnant or who suspect that they are pregnant during the study must report the information to the investigator and discontinue study drug immediately. Subjects who become pregnant will be discontinued from the study and their study treatment assignment will be unblinded by the Investigator and provided to the subject.

Subjects who become pregnant while on study should receive appropriate monitoring and care until the conclusion of the pregnancy. Subjects who become pregnant while on study who are not engaged in pre-natal care that includes a routine second trimester ultrasound will be referred for ultrasonography as part of study follow-up. Instructions for reporting pregnancy and pregnancy outcome are outlined in Section [7.6.2.1](#).

**Appendix 7. Definitions of Stage 3 Opportunistic Illnesses in HIV
(CDC Guidelines)**

- 1) Candidiasis of bronchi, trachea, or lungs
- 2) Candidiasis of esophagus
- 3) Cervical cancer, invasive
- 4) Coccidioidomycosis, disseminated or extrapulmonary
- 5) Cryptococcosis, extrapulmonary
- 6) Cryptosporidiosis, chronic intestinal (> 1 month duration)
- 7) Cytomegalovirus disease (other than liver, spleen or nodes)
- 8) Cytomegalovirus retinitis (with loss of vision)
- 9) Encephalopathy, HIV-related
- 10) Herpes simplex: chronic ulcer(s) (> 1 month duration); or bronchitis, pneumonitis or esophagitis
- 11) Histoplasmosis, disseminated or extrapulmonary
- 12) Isosporiasis, chronic intestinal (> 1 month duration)
- 13) Kaposi's sarcoma
- 14) Lymphoma, Burkitt's (or equivalent term)
- 15) Lymphoma, immunoblastic (or equivalent term)
- 16) Lymphoma, primary, of brain
- 17) *Mycobacterium avium* complex or *Mycobacterium kansasii*, disseminated or extrapulmonary
- 18) *Mycobacterium tuberculosis*, of any site, pulmonary, disseminated or extrapulmonary
- 19) *Mycobacterium*, other species or unidentified species, disseminated or extrapulmonary
- 20) *Pneumocystis jirovecii* (previously known as "*Pneumocystis carinii*") pneumonia
- 21) Pneumonia, recurrent
- 22) Progressive multifocal leukoencephalopathy

23) *Salmonella* septicemia, recurrent

24) Toxoplasmosis of brain

25) Wasting syndrome attributed to HIV infection

CDC Stage-3-Defining Opportunistic Illnesses in HIV Infection - 2014 {[Selik 2014](#)}

Table 3-2	Analysis Windows for HIV-1 RNA, HBV DNA, CD4+ cell count, CD4%,	
	Hematology, Chemistry, Urinalysis, and Serum/Urine Pregnancy Laboratory Tests,	
	eGFR _{CG} , Vital Signs, Weight and BMI for the All B/F/TAF Analysis	19
Table 3-3.	Analysis Windows for HBV Serology for the Randomized Phase Analysis	20
Table 3-4.	Analysis Windows for HBV Serology for the All B/F/TAF Analysis	20
Table 3-5	Analysis Windows for Metabolic Assessments for the Randomized Phase Analysis	21
Table 3-6	Analysis Windows for Metabolic Assessments for All B/F/TAF Analysis	21
Table 3-7	Analysis Windows for Renal Function for the Randomized Phase Analysis	21
Table 3-8	Analysis Windows for HCV Serology and HCV RNA for the Randomized Phase	
	Analysis	22
Table 3-9	Analysis Windows for HCV Serology and HCV RNA Assessments for the All	
	B/F/TAF Analysis	22
Table 12-1.	Example Search Terms for "COVID-19" and "Virtual" Used to Identify	

Missed/Virtual Visits. 57

LIST OF ABBREVIATIONS

AE adverse event

ALP alkaline phosphatase
ALT alanine aminotransferase
ANOVA analysis of variance

ARV antiretroviral

AST aspartate aminotransferase

BIC bictegravir

B/F/TAF fixed dose combination of bictegravir (BIC; B) 50 mg / emtricitabine (FTC; F) 200 mg /

tenofovir alafenamide (TAF) 25 mg

BMI body mass index

CDER Center for Drug Evaluation and Research

CG Cockcroft-Gault
CI confidence interval

CMH Cochran-Mantel-Haenszel

CRF case report form
CSR clinical study report
DNA deoxyribonucleic acid
DTG dolutegravir, Tivicay®
ECG electrocardiogram

eCRF electronic case report form

eGFR estimated glomerular filtration rate

eGFR_{CG} estimated glomerular filtration rate using Cockcroft-Gault formula

FAS full analysis set

FDA Food and Drug Administration

FDC fixed dose combination

F/TAF fixed dose combination of emtricitabine (FTC; F)/ tenofovir alafenamide (TAF)

FTC, F emtricitabine

GFR glomerular filtration rate
Gilead Gilead Sciences, Inc.

GS-9883 bictegravir

HBcAb hepatitis B core antibody
HBeAb hepatitis B e-antibody
HBeAg hepatitis B e-antigen

HBsAb hepatitis B surface antibody HBsAg hepatitis B surface antigen

HBV hepatitis B virus
HCV hepatitis C virus
HCVAb hepatitis C antibody
HDL high density lipoprotein

HIV-1 human immunodeficiency virus (Type 1)

HLGT high level group term
HLT high level term
ID identification

IDMC independent data monitoring committee

IWRS interactive web response system

LDL low density lipoprotein

LLT lowest level term

MedDRA Medical Dictionary for Regulatory Activities

MH Mantel-Haenszel

PEP post-exposure prophylaxis
PrEP pre-exposure prophylaxis

PK pharmacokinetic
PP per protocol
PT preferred term
Q quartile
Q1 first quartile
Q3 third quartile

RBP retinol binding protein RNA ribonucleic acid

SAE serious adverse events
SAP statistical analysis plan
SD standard deviation

SMQ Standardised MedDRA Query

SOC system organ class
TAF tenofovir alafenamide

TDF tenofovir disoproxil fumarate
TFL tables, figures, and listings

TFV tenofovir

ULN upper limit of normal WHO World Health Organization

1. INTRODUCTION

This statistical analysis plan (SAP) describes the statistical analysis methods and data presentations to be used in tables, figures, and listings (TFLs) of the final analysis for Study GS-US-380-4458, which will be performed when all participants have completed the study or prematurely discontinued from the study drug. This SAP is based on the study protocol amendment 2 dated 06 July 2018 and the electronic case report form (eCRF). The SAP will be finalized before database finalization for the interim analysis. Any changes made after the finalization of the SAP will be documented in the clinical study report (CSR).

1.1. Study Objectives

The primary objectives of this study are:

- To evaluate the efficacy of fixed dose combination (FDC) of bictegravir /emtricitabine /tenofovir alafenamide (BIC/FTC/TAF; B/F/TAF) versus a regimen of dolutegravir (DTG) + emtricitabine/tenofovir disoproxil fumarate (FTC/TDF; F/TDF) in HIV and HBV treatment naïve, HIV-1 and HBV co-infected participants as determined by the achievement of HIV-1 RNA < 50 copies/mL at Week 48
- To evaluate the efficacy of FDC of B/F/TAF versus DTG + F/TDF in HIV and HBV treatment naïve, HIV-1 and HBV co-infected participants as determined by the proportion of participants with plasma HBV DNA < 29 IU/mL at Week 48

The secondary objectives of this study are:

- To evaluate the efficacy of FDC of B/F/TAF versus DTG + F/TDF as determined by the achievement of HIV-1 RNA < 50 copies/mL at Week 96
- To evaluate the efficacy of FDC of B/F/TAF versus DTG + F/TDF as determined by the proportion of participants with plasma HBV DNA < 29 IU/mL at Week 96
- To evaluate the efficacy of the FDC of B/F/TAF versus DTG + F/TDF as determined by the proportion of participants with ALT normalization at Weeks 48 and 96
- To evaluate the efficacy of FDC of B/F/TAF versus DTG + F/TDF as determined by the proportion of participants with HBsAg loss at Weeks 48 and 96
- To evaluate the safety and tolerability of the two treatment groups through Week 96

1.2. Study Design

Design Configuration and Participant Population

Study GS-US-380-4458 is a randomized, double-blinded, multicenter, active-controlled study to evaluate the safety and efficacy of B/F/TAF FDC versus DTG + F/TDF FDC in treatment-naïve, HIV-1 and HBV co-infected adult participants.

Treatment Groups

Participants who provide written consent and meet all eligibility criteria will be randomized in a 1:1 ratio to one of the following 2 treatment groups:

- Treatment Group 1 (n=120): FDC of BIC 50 mg/FTC 200 mg/ TAF 25 mg + placebo to match DTG 50 mg + placebo to match FDC of FTC 200 mg/TDF 300 mg administered orally, once daily, without regard to food
- Treatment Group 2 (n=120): DTG 50 mg + FDC of FTC 200 mg/TDF 300 mg + placebo to match FDC of B/F/TAF administered orally, once daily, without regard to food

Key Eligibility Criteria

Participants must meet all of the following inclusion criteria to be eligible to participate in the study:

- HIV-1 co-infection:
 - 1) Must be HIV antiretroviral treatment naïve with plasma HIV-1 RNA ≥ 500 copies/mL at screening
 - 2) \leq 10 days of prior therapy with any antiretroviral agent, including lamivudine and entecavir, following a diagnosis of HIV-1 infection (except the use for PrEP or PEP, up to one month prior to screening)
 - 3) Screening genotype report must show sensitivity to FTC and TFV. This report will be provided by Gilead Sciences. Alternatively, if genotype results from a local laboratory obtained ≤ 90 days prior to screening visit date show sensitivity to these drugs, this genotype will be acceptable to fulfill this inclusion criterion in the event that the genotype obtained at screening is not yet available and all other inclusion/exclusion criteria have been confirmed
- HBV co-infection:
 - 4) Must be HBV treatment naïve (defined as < 12 weeks of oral antiviral treatment)
 - 5) Screening HBV DNA ≥ 2,000 IU/mL
- Estimated glomerular filtration rate (eGFR) ≥ 50 mL/min according to the Cockcroft-Gault (C-G) formula (at the screening visit)

Study Periods/Phases

After screening, eligible participants will be treated for at least 96 weeks during the blinded treatment phase. Following the Screening and Day 1 visits, participants will be required to return for study visits at Weeks 4, 8, 12 and every 12 weeks thereafter.

Once all participants complete their Week 96 visit and Gilead completes the Week 96 analysis, all participants will return to the clinic (preferably within 30 days) for an End of Blinded Treatment Visit. At the End of Blinded Treatment Visit, if safety and efficacy of the B/F/TAF FDC is demonstrated for the HIV-1 and HBV coinfected participants following review of unblinded data, participants in a country where the B/F/TAF FDC is not available will be given the option to receive the B/F/TAF FDC in an open label (OL) extension phase for up to 48 Weeks or until the product becomes accessible to participants through an access program, or until Gilead Sciences elects to discontinue the study in that country, whichever occurs first.

All participants participating in the OL extension phase, without regard to their blinded treatment regimen, will return for study visits at Week 12 OL and every 12 weeks thereafter.

Participants who complete the study through the End of Blinded Treatment Visit and do not continue on the OL extension phase, will be required to return to the clinic 30 days after the End of Blinded Treatment Visit for a 30-Day Follow-Up Visit.

Treatment assignments will be provided to the investigators within 30 days of the last participant completing the End of Blinded Treatment Visit.

Schedule of Assessments

After screening procedures, eligible participants will be randomized 1:1 to Treatment Group 1 or Treatment Group 2 and treated for 96 weeks. Following the Day 1 visit, participants will be required to return for study visits at Weeks 4, 8, and 12, and then every 12 weeks from Week 12 through Week 96. After Week 96, all participants will continue to take their blinded study drugs and attend a study visit every 12 weeks until the End of Blinded Treatment Visit.

Laboratory analyses (serum chemistry, liver function tests, hematology, urinalysis, pregnancy testing [for females of childbearing potential]), will be performed at the Screening, Day 1, and all subsequent study visits. HIV-1 RNA and CD4 + cell count will be performed at Screening, Day 1, and all subsequent study visits. HIV-1 genotype (RT and PR) will be determined at screening. Plasma HBV DNA levels, HBV serology (HBsAg and reflex anti-HBs Ab, and HBeAg and reflex anti-HBe Ab) will be performed at Screening, Day 1, and every 12 weeks thereafter. Plasma HBV DNA will be monitored at all study visits.

Serum samples for potential sequence analysis of HBV polymerase/reverse transcriptase (pol/RT) should be collected at all time points except screening. Sequencing analysis of the HBV pol/RT will be attempted for all viremic participants (HBV DNA > 69 IU/mL) at Weeks 48, 96 or early study drug discontinuation as early as Week 8, as well as all participants who meet virologic breakthrough criteria.

Adverse events and concomitant medications will be assessed at each visit.

More details for study procedures may be found in Appendix 1.

Pharmacokinetics

A blood sample for pharmacokinetics (PK) trough analysis will be obtained 20 to 28 hours following the last dose at Weeks 4, 12, and 36. Following an observed dose, one post-dose PK blood sample will be collected between 1 and 4 hours postdose at Weeks 8 and 24.

Randomization

Participants will be randomized in a 1:1 ratio to 1 of 2 Treatment Groups (Treatment Group 1: Treatment Group 2). Randomization will be stratified by HBeAg (positive vs negative), HBV DNA (< $8 \log_{10} IU/mL$ vs $\geq 8 \log_{10} IU/mL$), CD4+ cell count (< $50 \text{ cells/}\mu L$ vs $\geq 50 \text{ cells/}\mu L$) at screening.

Site and/or Stratum Enrollment Limits

Approximately 70 study sites worldwide participated. There was no enrollment limit for individual sites.

Study Duration

The randomized, double-blind phase of this study is at least 96 weeks in duration.

1.3. Sample Size and Power

A total of approximately 240 HIV-1 and HBV co-infected participants, randomized in a 1:1 ratio to 2 treatment groups (120 participants per treatment group), achieves 90% power to detect a non-inferiority margin of 12% in Week 48 response rate (HIV-1 RNA < 50 copies/mL as defined by the US FDA-defined snapshot algorithm) difference between the 2 treatment groups. For the sample size and power computation, it is assumed that both treatment groups have a response rate of 91% (based on Gilead Studies GS-US-380-1489 and GS-US-380-1490), that the non-inferiority margin is 12%, and that the significance level of the test is at a one-sided 0.025 level.

A total of approximately 240 participants also provides 81% power to detect a non-inferiority margin of 12% with respect to the co-primary efficacy endpoint of the proportion of participants with plasma HBV DNA < 29 IU/mL at Week 48. This assumes that both treatment groups have a response rate of 88% (based on Gilead Studies GS-US-320-0108 and GS-US-320-0110), that the non-inferiority margin is 12%, and that the significance level of the test is at a one-sided 0.025 level.

2. TYPE OF PLANNED ANALYSIS

2.1. Data Monitoring Committee Analyses

The Week 24 Independent Data Monitoring Committee (IDMC) analysis was conducted after all participants enrolled completed their Week 24 visit or prematurely discontinued from the study drug. The purpose of this interim analysis was to provide the IDMC with a statistical report for review. More details are documented in the IDMC charter.

2.2. Interim Analyses

2.2.1. Week 48 Analysis

The Week 48 analysis was conducted after all participants either completed their Week 48 visit or prematurely discontinue from the study drug.

2.2.2. Week 96 Analysis

The Week 96 analysis was conducted after all participants either completed their Week 96 visit or prematurely discontinued from the study drug.

2.2.3. Final Analysis

The final statistical analysis will be conducted after all participants either complete the study or prematurely discontinue from the study.

This statistical analysis plan describes the analysis plan for the final analysis.

3. GENERAL CONSIDERATIONS FOR DATA ANALYSES

The Final Analysis will include two sets of analysis: randomized phase analysis and all B/F/TAF analysis. All table summaries in this final analysis will be based on data included in the All B/F/TAF analysis (eg, data collected during the study period when participants were on B/F/TAF).

Randomized phase analysis (eg, including data collected during double-blind phase when participants were on the double-blind study drug), and the corresponding analysis window defined in Section 3.8, will be used to support applicable listings where data collected from the double-blind phase are indicated. The wording of randomized phase or double-blind phase might be used interchangeably throughout the SAP and in the TFLs.

Randomized Phase Analysis:

- For participants who are never treated in the extension phase of the study, including those who prematurely discontinue the randomized study drug or who complete the randomized study drug and do not receive any dose of B/F/TAF in the extension phase, all available data will be included in the randomized phase analysis.
- For participants who complete the randomized phase and receive at least 1 dose of B/F/TAF in the extension phase, the randomized phase analysis will include (1) all available AE, concomitant medication, pregnancy, and death data collected prior to the extension phase first dose date; (2) all available other data, such as laboratory, vital sign, electrocardiogram (ECG), collected on or prior to the extension phase first dose date.

All B/F/TAF Analysis:

- For participants who receive B/F/TAF in the randomized phase, all available data for participants who actually receive B/F/TAF in the randomized phase will be included.
- For participants who actually receive DTG + F/TDF in the randomized phase and receive at least 1 dose of B/F/TAF in the extension phase, (1) all available AE, concomitant medication, pregnancy, and death data with start date **on or after** the first dose date of B/F/TAF in the extension phase and (2) all available other data, such as laboratory, vital sign, and ECG data, collected **after** the first dose date of B/F/TAF in the extension phase will be included. The data collected **on or prior to** the first dose date of B/F/TAF will be used to derive the baseline value for the all B/F/TAF analysis.

Note that all data for participants who actually receive DTG + F/TDF in the randomized phase and do not receive any dose of B/F/TAF in the extension phase will be excluded from all B/F/TAF analysis. The actual treatment received will differ from the randomized treatment only when the actual treatment received differs from randomized treatment for the entire treatment duration.

Analysis results will be presented using descriptive statistics. For categorical variables, the number and percentage of participants in each category will be presented; for continuous variables, the number of participants (n), mean, standard deviation (SD) or standard error (SE), median, first quartile (Q1), third quartile (Q3), minimum, and maximum will be presented.

For the All B/F/TAF analysis, no statistical comparison between treatment groups will be conducted.

By-participant listings will be presented for all participants in the all randomized analysis set unless otherwise specified, and sorted by participant ID number, visit date, and time (if applicable). Data collected on log forms, such as AEs, will be presented in chronological order within a participant. The treatment group to which participants were randomized will be used in the listings. Most listings will be provided for the all randomized analysis set for data from both phases of the study. Some listings for the all B/F/TAF safety analysis set will also be provided.

In general, age (in years) on the date of the first dose of study drug will be used for analyses and presentation in listings. For randomized but never dosed participants, age on the date of randomization will be used. For screen failures, age on the date of the informed consent was signed will be used. If only birth year is collected on the eCRF, "01 January" will be used for the unknown birth day and month for the purpose of age calculation, similarly, if only birth year and month are collected on the eCRF, "01" will be used for the unknown birth day for the purpose of age calculation.

In general, permanent discontinuation of the randomized study drug refers to premature discontinuation of the randomized study drug or completion of the randomized study drug. Similarly, permanent discontinuation of the extension phase study drug refers to premature discontinuation of the extension phase study drug or completion of the extension phase study drug. More specifically, for the randomized phase analysis, study drug refers to the randomized study drugs (B/F/TAF or DTG + F/TDF); for the all B/F/TAF analysis, study drug refers to B/F/TAF.

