8.6. Safety Analysis

All safety analyses will be performed using the safety analysis set.

All safety data collected on or after the date that the study drug was first administered up to the date of the last dose of study drug plus 30 days, unless specified otherwise will be summarized for subjects in the safety analysis set according to the study drug received.

Data for the pretreatment period and the period post the date of last dose of study drug plus 30 days will be included in data listings for all enrolled subjects.

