3.1.3. All B/F/TAF Safety Analysis Set

The All B/F/TAF Safety Analysis Set will include all participants who (1) are randomized into the study and (2) have received at least 1 dose of the B/F/TAF in the randomized phase or at least 1 dose of the B/F/TAF in the extension phase. This is the primary analysis set for the all B/F/TAF safety analyses.

For safety analyses, all safety data collected up to 30 days after permanent discontinuation of B/F/TAF (including randomized and open label phases) will be included in the safety summaries, unless specified otherwise.

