7.8. Changes From Protocol-Specified Safety Analyses

No change from the protocol-specified safety analysis is planned.

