- r After Week 96, all participants will continue to take their blinded study drug and attend visits every 12 weeks until the End of Blinded Treatment Visit. Visit window of ± 6 days for study visits post Week 96.
- s Open label study drug, B/F/TAF FDC will be dispensed to participants participating in the Open-Label Rollover extension.
- t HBV serology (HBsAg and reflex anti-HBs Ab, and HBeAg and reflex anti-HBe Ab). After Week 96, HBV serology will be performed every 24 weeks.
- u Hepatitis C virus (HCVAb) serology. Participants who are HCVAb positive will have a HCV RNA test performed. After Week 96 visit, testing to be performed every 48 weeks.
- v Randomization may be performed up to 3 days prior to the in-clinic Day 1 visit provided that all screening procedures have been completed and participant eligibility has been confirmed.
- w Genotypic analysis of HBV polymerase/reverse transcriptase (pol/RT) for resistance surveillance will be attempted for all participants who remain viremic (HBV ≥ 69 IU/mL) at Week 48 and 96 (or early study drug discontinuation visit as early as Week 8) and for those with virologic breakthrough as defined in Protocol Section 6.15.

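### The final SAP tabulates safety on B/F/TAF exposure only, so DTG + F/TDF safety data collected after the Week 96 cut are listed but not summarised

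*SAP*

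**What the plan says.** SAP Section 3 defines a randomised phase analysis and an All B/F/TAF analysis, then limits the tables to the second: "All table summaries in this final analysis will be based on data included in the All B/F/TAF analysis". The randomised phase analysis "will be used to support applicable listings where data collected from the double-blind phase are indicated".

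The two arms enter the tables differently. For the B/F/TAF arm, "all available data for participants who actually receive B/F/TAF in the randomized phase will be included". Participants who received DTG + F/TDF and took open-label B/F/TAF contribute only from the first open-label dose, with a new baseline, in a column labelled as the switch group (SAP 3.2 and 3.8.1). Those who received DTG + F/TDF and "do not receive any dose of B/F/TAF in the extension phase will be excluded from all B/F/TAF analysis". SAP 3.1.3 builds this into the safety set, whose members must "have received at least 1 dose of the B/F/TAF in the randomized phase or at least 1 dose of the B/F/TAF in the extension phase". SAP Section 7 ties the 30-day post-treatment window to stopping B/F/TAF.

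Protocol 8.6 says that safety data from first dose to last dose plus 30 days "will be summarized for subjects in the safety analysis set according to the study drug received", subject to exceptions specified elsewhere. Protocol 8.2.1.3 sets the same window with the same allowance. SAP 7.8 reports: "No change from the protocol-specified safety analysis is planned".

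**The concern.** Randomised, blinded follow-up does not end at Week 96. Data collected between the Week 96 cut and the end of blinded dosing, and in the 30 days after it for those who do not roll over, cannot be in the Week 96 report. The final analysis is the last chance to summarise them by arm.

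As written, late adverse events, serious adverse events, deaths, Grade 3–4 laboratory abnormalities and eGFR changes on B/F/TAF are counted in tables with no concurrent randomised column beside them. The only other column is the switch group, on open-label drug, from a reset baseline and at a later point in follow-up. A reader who wants to know whether a late event rate on B/F/TAF is unusual would have to count DTG + F/TDF events from listings and construct a denominator.

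**Working it through.** No figure in the plan needs reproducing here. The check is a comparison of text, followed by an illustration of scale.

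**Do the data exist?** SAP Appendix Table 1 (note r) states: "After Week 96, all participants will continue to take their blinded study drug and attend visits every 12 weeks until the End of Blinded Treatment". The endpoint meant is the visit of that name. Protocol 3.4, note b, says the same. Protocol 6.6.1 words the endpoint as the last subject's Week 96 visit, but Protocol 6.6.2 places the End of Blinded Treatment Visit after both that visit and completion of the Week 96 analysis, and open-label drug is first dispensed there. Under Protocol 6.8.2, completers who do not roll over return 30 days after stopping drug. SAP 2.2.2 records the Week 96 analysis as already conducted. Comparator data after that cut therefore arise by design.

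**Where do they go?**

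| Safety data after the Week 96 cut | B/F/TAF arm | DTG + F/TDF arm |
|---|---|---|
| Blinded phase | Tabulated | Listed only |
| 30 days after last blinded dose, no rollover | Tabulated | Listed only |
| From first open-label dose | Tabulated | Tabulated, as the switch group |

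**Is this covered elsewhere?** SAP 4.1.1 says enrolment was summarised at Week 48, and SAP Section 6 says the Week 48 and 96 efficacy endpoints were reported earlier. There is no matching statement for safety. Blinded data from before the Week 96 cut may have been tabulated in the Week 96 report; data after it could not have been.

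**How much?** The documents give neither the interval from the cut to the end of blinded dosing nor the number still on drug. SAP Appendix 3 gives 243 in the safety analysis set, without a split by arm. Assumptions:

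- N = 243 / 2 = 121.5 on DTG + F/TDF
- r = 0.80 to 0.95 still on blinded drug at the cut
- w = 4 to 48 weeks from the cut to the end of blinded dosing

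On-drug person-years = N × r × w / 52.18:

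- Low: 121.5 × 0.80 × 4 / 52.18 = 7.5
- w = 12: 22.4 (r = 0.80) to 26.5 (r = 0.95)
- w = 24: 44.7 to 53.1
- High: 121.5 × 0.95 × 48 / 52.18 = 106.2

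Adding 30 days (30/7 = 4.29 weeks) for everyone gives 121.5 × 0.80 × (4 + 30/7) / 52.18 = 15.4 to 121.5 × 0.95 × (48 + 30/7) / 52.18 = 115.7. These overstate the total to the extent that participants roll over, because their data from the first open-label dose are tabulated.

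**The case against.** The sponsor has a reasonable reply. Both protocol sentences allow exceptions, and the safety objective compares the two groups through Week 96, so the formal comparison belongs to an analysis already done. The comparator data are also accessible. Most listings cover all randomised participants in both phases, including adverse events, deaths, laboratory abnormalities and ALT elevations. SAP Appendix 7 applies treatment-emergent rules to randomised-phase data. The disposition table (SAP 4.1.2) covers both arms, with reasons for stopping blinded drug.

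Most of this stands. It means the restriction is open to the sponsor, and that late discontinuations are visible side by side. It does not explain why SAP 7.8 reports no change, since neither protocol sentence stops at Week 96. Nor does it give the late B/F/TAF counts a concurrent comparator.

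A reader might also infer that hepatitis B exacerbation after stopping drug is tabulated for B/F/TAF and not for DTG + F/TDF. The documents do not support that. SAP 7.2.4 pools all values to 30 days after last dose and counts each participant once for each individual test, at the most severe value, so off-drug elevations cannot be told from on-drug ones. SAP 7.2.5 summarises ALT elevations only to 1 day after last dose. No planned table isolates post-stopping exacerbation in either arm.

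**Conclusion.** The point holds for safety data after the Week 96 cut. DTG + F/TDF blinded-phase data from that period, and the 30-day follow-up of DTG + F/TDF completers who do not roll over, are listed only, while the same data on B/F/TAF are tabulated. This departs from the default in Protocol 8.2.1.3 and 8.6, and SAP 7.8 does not declare it.

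It should not be read as a flat breach, given the allowance for exceptions in both sections. Nor should it be read as saying that all comparator follow-up goes untabulated: the post-treatment gap concerns non-rollovers, whose number is not given, and data before the cut may be in the Week 96 report, whose SAP is not among the documents. The size, about 7–106 on-drug person-years, rests wholly on the assumed arm size, retention and interval. The Week 48 and Week 96 efficacy conclusions are unaffected.

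**What to change.** In SAP Sections 3 and 7, add randomised-phase safety tables by drug received, with B/F/TAF and DTG + F/TDF side by side, from first dose to last blinded dose plus 30 days, or to the first open-label dose for participants who roll over. Cover the adverse event overview, serious adverse events, deaths, adverse events leading to discontinuation, Grade 3–4 laboratory abnormalities, the liver tests of 7.2.4, the ALT elevations of 7.2.5, and serum creatinine and eGFR. Keep the All B/F/TAF tables as the second set. Correct SAP 7.8 to state and justify any restriction that remains.

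The ingredients are already specified: randomised-phase data rules (Section 3), analysis windows (Table 3-1), and randomised-phase laboratory flags and treatment-emergent rules (Appendix 7). The cost is a small amount of extra programming and SAP wording, with no new data. These tables would not by themselves isolate hepatitis flares after stopping drug.
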